6.2 Statistical analysis plan

6.2.1 General considerations

The statistical analyses and reporting will adhere to the CONSORT guidelines.^{42,43} All tests will be two-sided, a p-value < 0.05 will be considered significant, and all confidence intervals will have 95% coverage. All analyses will be conducted on a modified intention-to-treat basis only including participants receiving at least the first dose of the study medications. In a double-blind trial, this approach is unbiased while increasing precision.⁴⁴ The two groups will be compared in relation to baseline characteristics using descriptive statistics.

The persons conducting the statistical analysis will be blinded to the randomized allocation. Groups will be designated as “A” and “B” until all pre-specified analyses are performed and shared with all authors and the Data Safety Monitoring Board.

6.2.2 Creatinine at 72-hours

Assuming no unbalanced potentially confounding variables (as would be expected in this randomized trial), we will compare repeated measures of creatinine levels at each time point (0h, 24h, 48h, 72h) between arms using repeated measures analysis. A compound symmetry covariance structure will be used. If a patient receives renal replacement therapy or dies before any time point, creatinine levels will be imputed by carrying forward the last known value before the event. Study site will be controlled for as a fixed-effect in the regression model.

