1.5 Thiamine may attenuate renal injury in patients with septic shock. In a *post-hoc* analysis of data collected during a randomized trial of thiamine vs. placebo,³ patients who received thiamine were less likely to require renal replacement therapy (RRT) and had lower creatinine levels over time as compared to patients who received placebo.⁴ That study, however, was limited by its *post-hoc* design, an imbalance in premorbid renal function between groups, and inconsistency with regards to the timing of biomarker measurement. In a non-randomized observation study of patients with severe sepsis or septic shock at a single center, those who received the combination of thiamine, vitamin C, and hydrocortisone were less likely to require RRT as compared to historical controls at the same site (3/31 [10%] vs. 11/30 [33%], $p=0.02$).²⁶ This study likewise provides some support for thiamine as a renal protective agent in sepsis, but is limited by its quasi-experimental design and the associated potential for bias.

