2.2 Allocation

Participants will be randomized in a 1:1 ratio to either thiamine or placebo in blocks with random sizes of 2 or 4. The randomization will be stratified according to site.³⁸ An independent statistician will create the randomization list using a random number generator. The complete list will only be shared with an independent pharmacy consultant, who will not be involved in clinical care. The pharmacy consultant and the independent statistician will both store the randomization list.

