3.3 Exclusion criteria

Exclusion criteria:

- 1) Clinical indication for thiamine administration (alcoholism, known or highly suspected deficiency) or treatment with thiamine beyond the amount found in a standard multivitamin within the last 10 days
- 2) Renal replacement therapy within the past 30 days
- 3) Comfort measures only or anticipated withdrawal of support within 24 hours
- 4) Protected populations (pregnant women, prisoners)
- 5) Known thiamine allergy

Justification of Inclusion and Exclusion Criteria: The inclusion criteria reflect the definition of septic shock put forth by the Society of Critical Care Medicine and European Society of Intensive Care Medicine Task Force.¹⁶ We will include only patients with a creatinine of >1.0 mg/dL to ensure we are evaluating a true 'at-risk' population for kidney injury. The trial end-points cannot be assessed in patients already receiving renal replacement therapy, and this population will therefore be excluded. We have chosen to include adult patients only due to differences in etiology and treatment of septic shock in children. Also, BIDMC does not have a pediatric unit. We will exclude patients who are presently receiving or who will likely receive supplemental thiamine for clinical purposes as we feel it would be unethical to randomize these patients to the placebo arm. We will also exclude patients with a known thiamine allergy.

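### Section 6.2.2 makes the primary creatinine model conditional on observed balance and adjusts for site only; a prespecified renal-history covariate would be better

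*Protocol*

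**What the plan says.** - **Primary model (protocol, 6.2.2).** Creatinine at 0, 24, 48 and 72 hours is compared between arms by repeated measures analysis. The section begins "Assuming no unbalanced potentially confounding variables (as would be expected in this randomized trial" and ends "Study site will be controlled for as a fixed-effect in the regression model". It names no other covariate, and no alternative if the opening condition is not met.
- **Motivating evidence (1.5).** The limitations of the post-hoc analysis of the earlier randomised thiamine trial are its post-hoc design, "an imbalance in premorbid renal function between groups", and inconsistent timing of biomarker measurement.
- **Eligibility (3.2, 3.3).** A single creatinine threshold applies, justified as "to ensure we are evaluating a true 'at-risk' population for kidney injury". The only renal exclusion is "Renal replacement therapy within the past 30 days". There is no reference to a pre-illness creatinine or to chronic kidney disease.
- **Allocation (2.2).** "The randomization will be stratified according to site", with a 1:1 ratio and random blocks of 2 or 4. Site is the only stratification factor.
- **Other relevant text.** The synopsis, 2.1 and 5.1.1 word the primary outcome as a change in creatinine. Section 6.2.1 has baseline characteristics compared descriptively and keeps the analysts blinded to arm. Section 7.2 leaves the list of variables to the case report form.

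**The concern.** A patient with long-standing stable creatinine elevation and one whose creatinine rose with the septic episode can enter with the same 0 h value. They may then follow different courses over 72 hours: the second has an acute rise that may resolve or worsen, the first may not. The 0 h measurement, taken during shock, cannot tell them apart.

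The protocol recognises premorbid renal function as important enough to weaken the earlier analysis, but does not carry it into stratification or the model. Instead, 6.2.2 states the model on the premise that nothing is unbalanced. If the arms turn out to differ in renal history, the text as written supports neither keeping the site-only model nor any particular adjusted one. An adjustment introduced at that stage would look data-driven, and leaving it out would invite the objection that the protocol itself raises about its predecessor.

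**Working it through.** The protocol gives no figure for expected balance, so there is no stated number to reproduce here. The check asks how often a visible imbalance would arise, and how far it could move the primary contrast.

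**Inputs**
- 44 per arm, target difference 0.51 mg/dL, within-subject variance 0.19: section 6.1.
- Prevalence of chronic kidney disease of 20%, 30% or 40%: assumed, not in the protocol.
- Difference in mean 72-hour change between patients with and without chronic kidney disease of 0.3, 0.5 or 1.0 mg/dL: assumed, not in the protocol.

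**Step 1. Chance of imbalance.** Take the number with chronic kidney disease in each arm as independent Binomial(44, p). Since 4/44 = 9.1% and 5/44 = 11.4%, a gap of at least 10 points means 5 or more patients. Likewise, at least 15 points means 7 or more (7/44 = 15.9%), and at least 20 points means 9 or more (9/44 = 20.5%).

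| Assumed prevalence | Gap ≥10 points | Gap ≥15 points | Gap ≥20 points |
|---|---|---|---|
| 20% | 0.229 | 0.082 | 0.023 |
| 30% | 0.295 | 0.130 | 0.047 |
| 40% | 0.327 | 0.157 | 0.064 |

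At 10% prevalence the chance of a 10-point gap falls to 0.108.

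**Step 2. Effect on the 72-hour contrast.** Shift = (gap in proportion) × (difference in mean change). The table uses the smallest gaps that meet the first two thresholds.

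| Assumed difference in change (mg/dL) | Gap 5/44 | Gap 7/44 |
|---|---|---|
| 0.3 | 0.03 | 0.05 |
| 0.5 | 0.06 | 0.08 |
| 1.0 | 0.11 | 0.16 |

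As a share of 0.51, this runs from 0.034/0.51 = 7% to 0.159/0.51 = 31%.

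**Step 3. Compare with sampling error.** Under the stated compound symmetry structure, a within-patient change has variance 2 × 0.19 = 0.38. The standard error of the arm difference in change is √(2 × 0.38/44) = 0.13 mg/dL. Five of the six shifts lie below it. Only the largest (0.16) exceeds it, and that needs both a 15-point gap and a 1.0 mg/dL difference in course.

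A visible imbalance is therefore fairly likely, but one large enough to alter the conclusion is much less so.

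**The case against.** The strongest reply is that randomisation already deals with this. Standard errors and type I error allow for chance imbalance in every covariate, measured or not, so a site-only model is valid. That stands. A reader might infer that the earlier flaw would recur here as a bias; the documents do not support that. Section 1.5 attaches the imbalance to a post-hoc analysis, and the protocol does not show whether that analysis kept the full randomised set. It is no evidence that randomisation fails at this size.

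A second reply is that the 0 h creatinine is in the model and the outcome is worded as a change, so differences in starting level are partly handled. This also stands, and it would be wrong to say that the plan has no control for renal function at all. What remains is a different course from the same starting value. The control is only partial because 6.1 targets the mean level at 72 hours and 6.2.2 speaks of comparing levels at each time point.

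A reader might also point to the between-subject variance of 1.3 against 0.19 within subjects (6.1) as proof that renal history dominates. It is not. That component describes stable level, which a change contrast cancels, and says nothing about how chronic kidney disease affects the 72-hour course.

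Finally, the case report form may already collect renal history, a separate analysis plan may list covariates, and blinding of the analysts limits adjustment driven by the treatment result. All fair. The point therefore does not rest on anything being unrecorded. It rests on what 6.2.2 does state: a model premised on balance, with one covariate and no stated consequence if the premise fails. Blinding to arm labels does not prevent a covariate from being chosen because groups A and B differ on it.

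**Conclusion.** The point holds as a matter of precision, credibility and prespecification. The test in 6.2.2 is not biased, and nothing here invalidates the design. The defect is that the primary model depends on a balance condition that a trial of 44 per arm may well not appear to meet for the one prognostic factor the protocol singles out: about 23% to 33% for a 10-point gap in chronic kidney disease, and 8% to 16% for a 15-point gap.

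The likely shift in the contrast is modest, about 0.03 to 0.16 mg/dL against 0.51. These figures rest on an assumed prevalence of 20% to 40%, assumed differences in course of 0.3 to 1.0 mg/dL, and all 44 patients per arm being analysed. If chronic kidney disease is rarer, or has little bearing on the 72-hour course, the gain from adjustment is smaller still. The change is worth making because it is cheap and settles the question before any data are seen.

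**What to change.** In section 6.2.2, delete the opening condition about unbalanced confounders. Prespecify chronic kidney disease history (yes/no, taken from the medical record before randomisation) as a covariate alongside site in the primary model, to be included whatever balance is observed. If the case report form does not already hold that field, add it.

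Cost: protocol wording, one record field and one degree of freedom. Some histories will be misclassified, which weakens the adjustment but does not threaten validity because the variable is fixed before randomisation. Sample size, eligibility, stratification and treatment are unchanged.

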Primary outcome	Change in creatinine over the first 72-hours after enrollment
Key secondary outcomes	
• Incidence of renal failure requiring renal replacement during index ICU stay• Length of ICU stay• Hospital mortality

STEERING COMMITTEE

[name].

Attending, Pulmonary and Critical Care Medicine
Beth Israel Deaconess Medical Center
Harvard Medical School

[name].

Associate Professor of Medicine
Director, Center for Resuscitation Science
Beth Israel Deaconess Medical Center
Harvard Medical School

[name]

Assistant Professor of Emergency Medicine
Beth Israel Deaconess Medical Center
Harvard Medical School

[name].

Assistant Professor of Medicine
Beth Israel Deaconess Medical Center
Harvard Medical School

[name].

Instructor in Emergency Medicine
Beth Israel Deaconess Medical Center
Harvard Medical School

[name]

Associate Professor of Medicine
Beth Israel Deaconess Medical Center
Harvard Medical School

Conflicts of interest

The members of the steering committee have no financial conflicts of interest related to the current trial.

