2. TRIAL DESIGN

2.1 Overview

This will be an investigator-initiated, randomized, placebo-controlled, parallel group, double-blind, superiority trial of thiamine vs. placebo in participants with septic shock. A total of 88 adult participants will be enrolled. The primary outcome will be the change serum creatinine between enrollment and 72-hours. Key secondary outcomes include the incidence of renal failure during the index ICU stay and survival at 30 days.

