5. OUTCOMES

5.1 Definitions

5.1.1 Primary Outcome

The primary outcome will be creatinine change over the first 72-hours after enrollment with a focus on the 72-hour creatinine measurement.

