6. SAMPLE SIZE CALCULATION AND STATISTICAL ANALYSIS PLAN

6.1 Sample size calculation

The planned sample size is based on the proposed primary outcome. In this longitudinal repeated measures study design, we have 4 time points, and are interested in measuring the effect of the intervention (thiamine) on the mean level of creatinine at the last time point (72-hours). We hypothesized that at 72-hours, the estimated mean difference (placebo-thiamine) would have similar magnitude as the pilot study's ⁴ observed mean difference (about 0.51). We used a linear mixed-effects model to estimate the parameters of the variance-covariance structure of the repeated measures data and used these estimates in obtaining the effect estimate of the mean difference at each of the 4 time points, with emphasis on 72-hours. We simulated the data using the estimated variance-covariance components from the pilot data which 0.19 for within-subject variance, and 1.3 for between-subject variance, and the estimated mean differences for the 4 time points from the pilot data. These data were put through a linear mixed effects model where linear contrasts were used for estimation at each time point. We then computed the non-centrality parameter and the corresponding F-statistic value. Together with the numerator and denominator degrees of freedom, the estimate of power at each time point was derived. Through different iterations of sample size, at N=80 (40 patients in each arm), we obtained a power of 0.80 at 72-hours. This method of power analysis for linear mixed-effects model was published in 2000.⁴¹ To account for drop-out and to

ensure adequate power at the end of the trial, we will plan to enroll a total of 88 patients (44 per arm).

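### The primary outcome is a change in creatinine, but the sample size and analysis use creatinine levels, and the protocol does not name the deciding contrast or the role of the 0 h value

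*Protocol*

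**What the plan says.** Three places define the outcome as a change. The Trial Overview table gives "Change in creatinine over the first 72-hours after enrollment". Section 2.1 states "The primary outcome will be the change serum creatinine between enrollment and 72-hours". Section 5.1.1 states "The primary outcome will be creatinine change over the first 72-hours after enrollment with a focus on the 72-hour creatinine measurement".

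Two places work with levels. Section 6.1 says the sample size rests on the primary outcome, then describes the investigators as "interested in measuring the effect of the intervention (thiamine) on the mean level of creatinine at the last time point (72-hours"). Section 6.2.2, headed as creatinine at 72 hours, says "we will compare repeated measures of creatinine levels at each time point (0h, 24h, 48h, 72h) between arms using repeated measures analysis". It adds "A compound symmetry covariance structure will be used" and "Study site will be controlled for as a fixed-effect in the regression model". Site is the only covariate named. The 0 h value appears only as one of the four compared responses.

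Section 1.5 lists among the weaknesses of the earlier post-hoc analysis "an imbalance in premorbid renal function between groups".

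**The concern.** The time point is settled: it is 72 h. Two things are not: whether the deciding contrast is the level at 72 h or the change from 0 h, and what the 0 h value does in the model. Under randomisation both contrasts have the same expected arm difference, so neither is biased. They are still different tests with different standard errors, and they can give different verdicts on the same data. If the choice is open when the data are seen, the deciding test can be picked afterwards.

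Read together, sections 6.1 and 6.2.2 most naturally point to an unadjusted 72 h level. That is valid, but it discards most of the information in a baseline measurement planned for every participant. Given how section 1.5 describes the earlier data, the handling of baseline should be fixed in advance.

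**Working it through.** **Inputs.** From section 6.1: between-subject variance 1.3, within-subject variance 0.19, difference 0.51, 40 per arm. From section 6.2.1: two-sided 0.05. Normal approximation throughout; power ≈ Φ(0.51/SE − 1.96).

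**Implied quantities.** Variance of one level = 1.3 + 0.19 = 1.49. Correlation between any two times = 1.3/1.49 = 0.872.

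**The plan's own figure.** Section 6.1 states power 0.80 at 40 per arm. That needs an SD of 0.51/(2.802 × √(2/40)) ≈ 0.81. The SD of a level is √1.49 = 1.221 and the SD of a change is √(2 × 0.19) = 0.616, so 0.80 matches neither. This does not prove 0.80 wrong, because the differences simulated at 0, 24 and 48 h are not given. It does mean the stated power cannot show which contrast was intended.

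**Three readings, 40 per arm.**

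| Contrast | SE | Power at 0.51 |
|---|---|---|
| 72 h level, 0 h unused | √(2 × 1.49/40) = 0.273 | 0.46 |
| 0–72 h change | √(2 × 2 × 0.19/40) = 0.138 | 0.96 |
| 72 h adjusted for 0 h | √(2 × 1.49 × (1 − 0.872²)/40) = 0.133 | 0.97 |

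The unadjusted level needs 2 × 1.49 × (1.96 + 0.842)²/0.51² ≈ 90 per arm for power 0.80.

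**Does the mixed model use baseline by itself?** No. Generalised least squares under compound symmetry, with free arm means at all four times, gives the 72 h contrast an SE of 0.273. Constraining the 0 h means to be equal between arms gives 0.133.

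**How often the choice changes the verdict.** The level and change statistics correlate √((1 − 0.872)/2) ≈ 0.25. In one million bivariate normal draws they disagree on significance in 9% of trials with no effect and in 52% at 0.51. At 0.51 almost all of this is change significant and level not.

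**Sensitivity to the 0–72 h correlation (assumed values), total variance held at 1.49.**

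| Correlation | Level: power | Change: SE, power | Adjusted: SE, power |
|---|---|---|---|
| 0.872 (implied) | 0.46 | 0.138, 0.96 | 0.133, 0.97 |
| 0.7 | 0.46 | 0.211, 0.67 | 0.195, 0.74 |
| 0.5 | 0.46 | 0.273, 0.46 | 0.236, 0.58 |

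**Sensitivity to the effect.** If part of the 0.51 was already present at 0 h in the pilot (size not stated, so assumed), the net effect is smaller:

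- 0.2 at baseline, net 0.31: power 0.21 (level), 0.61 (change), 0.64 (adjusted).
- 0.3 at baseline, net 0.21: power 0.12, 0.33 and 0.35.

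**Compound symmetry.** If correlation decays with time, a model with constant correlation understates the variance of a 0–72 h comparison. Assume AR(1) at 0.90 per day. The six pairwise correlations average (3 × 0.90 + 2 × 0.81 + 0.729)/6 = 0.8415. The true/model variance ratio for the change is (1 − 0.729)/(1 − 0.8415) = 1.71, so type I error = 2 × (1 − Φ(1.96/√1.71)) = 0.134. At 0.95 per day the ratio is 1.75 and the error 0.139. The contrast with 0 h means constrained equal is affected similarly, at about 0.13. The unadjusted level is not exposed in this way.

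**The case against.** The strongest reply is that the text mostly resolves itself. Section 5.1.1 puts the focus on 72 h, section 6.1 names the 72 h mean level, and section 6.2.2 carries 72 h in its heading. The expected arm difference is the same for level and change, and once 0 h is adjusted for, the two analyses coincide. On this view only precision and wording are at issue. That is fair as to the treatment effect being estimated. It does not remove the problem: the named outcome remains a change, no deciding contrast is stated, and the roughly twofold difference in SE can decide significance.

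Other points stand in part:

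- The size of the gain depends on a correlation of 0.872 that comes from a constant-correlation fit. At 0.5 the change has no advantage over the level. Adjustment still does better than both.
- The 52% disagreement is largely the power gap restated, not separate evidence.
- The large gain and the compound-symmetry warning pull against each other. Under AR(1) at 0.90 the 0–72 h correlation is 0.729, and power with the correct SE is 0.72 (change) and 0.78 (adjusted), not 0.96 and 0.97. The AR(1) values are assumptions with no source in the protocol.
- The imbalance noted in section 1.5 concerns premorbid renal function. Creatinine at 0 h is measured during shock, so adjusting for it need not correct that imbalance. The section shows why baseline matters, not that this covariate cures it.
- Section 6.2.2 opens by assuming no unbalanced confounders, which may hint at adjustment otherwise. It gives no rule, and adjustment that depends on observed imbalance is itself not pre-specified.
- Baseline parameterisation is often left to a separate SAP. Here section 6.2 is titled as the statistical analysis plan, and it conflicts with the protocol's own outcome definition.

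**Conclusion.** The concern holds, and it should be fixed. The outcome definition and the analysis disagree on change versus level, and the role of 0 h creatinine is not stated. On the protocol's variances the reading chosen moves power from 0.46 to 0.96 or 0.97. Those figures assume 40 evaluable per arm, a normal approximation, a correlation of 0.872, and that all of the 0.51 is treatment effect. Across the alternatives examined, the 72 h contrast adjusted for 0 h always has more power than the unadjusted level, though the margin narrows to 0.58 against 0.46 at a correlation of 0.5. The unadjusted analysis is inefficient, not biased. Compound symmetry is a smaller, separate matter that arises once the contrast uses 0 h. Confidence is high on the inconsistency and on the ranking; the exact gain depends on the assumptions above.

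**What to change.** Name one primary test and use the same wording in the Trial Overview and sections 2.1, 5.1.1, 6.1 and 6.2.2: the arm difference in creatinine at 72 h, adjusted for 0 h creatinine (as a covariate or with 0 h means constrained equal between arms) and for site, whatever imbalance is observed. Make the 24 h and 48 h comparisons supportive. Replace compound symmetry with an unstructured covariance, or use robust standard errors. Redo the power calculation in section 6.1 for that contrast, with the arm difference at 0 h set to zero and the assumed 0–72 h correlation stated.

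No new data are needed, since 0 h creatinine is already scheduled for every participant. The cost is aligned wording in five places, one redone calculation, and a few more covariance parameters: 6 for three post-baseline times or 10 for four, instead of 2.

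### The primary creatinine model is tied to compound symmetry, which the protocol cannot support; if it fails, the primary p-value can err either way, and an unstructured covariance is a cheap safeguard

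*Protocol*

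**What the plan says.** Protocol section 6.2.2 compares creatinine between arms at 0, 24, 48 and 72 hours by repeated measures analysis, with study site as a fixed effect. On the covariance it says only: "A compound symmetry covariance structure will be used". Section 6.2.3 uses the same sentence for lactate. After death or renal replacement therapy, "creatinine levels will be imputed by carrying forward the last known value before the event".

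The only covariance information is in section 6.1, which takes from the pilot data "0.19 for within-subject variance, and 1.3 for between-subject variance". No variance by visit and no correlation by time lag is given.

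The protocol describes the tested quantity in two ways. The trial overview has "Change in creatinine over the first 72-hours after enrollment", and section 2.1 has "The primary outcome will be the change serum creatinine between enrollment and 72-hours". Section 5.1.1 has "creatinine change over the first 72-hours after enrollment with a focus on the 72-hour creatinine measurement". Section 6.1 powers the trial on the mean level at 72 hours, and the title of section 6.2.2 also points to the 72-hour value. Both readings are therefore checked below.

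**The concern.** Compound symmetry uses two parameters: one variance for all four visits and one correlation for all six pairs of visits. In an acute illness the spread of creatinine may grow, shrink or peak over three days, and values 72 hours apart may be less alike than values 24 hours apart. The fitted model then averages over these differences, and the standard error of one particular contrast can be wrong.

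The two readings of the outcome are exposed differently. The change from 0 to 72 hours is sensitive both to fading correlation and to changing spread. The 72-hour level is sensitive only to changing spread. What is at stake is the validity of the primary p-value and confidence interval.

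**Working it through.** **Inputs from the protocol.** 44 patients per arm, two-sided 5%, four visits, difference 0.51 (sections 6.1 and 6.2.1). Within-subject variance is 0.19 and between-subject variance 1.3, so the total is 1.49. Read as a random-intercept model, the constant correlation is 1.3/1.49 = 0.872.

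**The protocol's own figure.** Section 6.1 states power 0.80 at 40 per arm. This was not reproduced from the two components.
- Level: SE = √(2 × 1.49/40) = 0.273; 0.51/0.273 = 1.87; power = Φ(1.87 − 1.96) ≈ 0.46.
- Change: variance 2 × 0.19 = 0.38; SE = √(2 × 0.38/40) = 0.138; 0.51/0.138 = 3.70; power = Φ(3.70 − 1.96) ≈ 0.96.

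That mismatch is a separate matter. It does mean that 0.872 rests on one reading of the components.

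**Inputs assumed.** The protocol does not give the true covariance, so a range is shown with the mean variance held at 1.49. Constant-correlation scenarios use 0.872; the fades average about 0.87.

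**Formula.** With balanced complete data and free arm-by-visit means, the compound-symmetry REML fit uses v, the mean of the four variances, and c, the mean of the six covariances.
- Change: model variance 2(v − c); true variance var(0 h) + var(72 h) − 2 cov(0 h, 72 h).
- Level: model variance v; true variance var(72 h).
- With R = true/model, the large-sample type I error is 2[1 − Φ(1.96/√R)].

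**Worked examples.**
- Lag correlations 0.895/0.865/0.815, change: mean correlation (3 × 0.895 + 2 × 0.865 + 0.815)/6 = 0.8717; R = (1 − 0.815)/(1 − 0.8717) = 1.44; 1.96/1.20 = 1.63; type I error 10.3%.
- SD rising linearly by 25%, level: relative variances 1, 1.174, 1.361, 1.5625, mean 1.274; R = 1.5625/1.274 = 1.23; 1.96/1.107 = 1.77; type I error 7.7%.
- SD pattern 1/1.3/1.3/1, level: mean relative variance (1 + 1.69 + 1.69 + 1)/4 = 1.345; R = 1/1.345 = 0.74, so the test is conservative.

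**Simulation.** 60,000 null trials per scenario, compound symmetry fitted, complete normal data, site omitted (Monte Carlo SE about 0.1 point):

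| Assumed true covariance | R, change | Type I error, change | Type I error, 72-h level |
|---|---|---|---|
| Compound symmetry | 1.00 | 4.9% | 5.0% |
| Lag correlations 0.885/0.865/0.845 | 1.21 | 7.4% | 5.1% |
| Lag correlations 0.895/0.865/0.815 | 1.44 | 10.3% | 5.0% |
| AR(1), r = 0.92 | 1.73 | 13.9% | 5.0% |
| SD rising 25% | 1.10 | 6.2% | 7.7% |
| SD rising 50% | 1.30 | 8.5% | 10.0% |
| SD falling from 1.25 to 1 | 1.10 | 6.2% | 2.7% |
| SD up 20% by 24 h, then flat | 0.97 | 4.6% | 5.9% |
| SD 1/1.2/1.2/1 | 0.76 | 2.7% | 3.2% |
| SD 1/1.3/1.3/1 | 0.65 | 1.4% | 2.4% |
| SD 1/1.2/1.2/1 with the 0.895/0.865/0.815 fade | 1.12 | 6.4% | 3.1% |
| SD 1/1.3/1.3/1 with the same fade | 0.95 | 4.6% | 2.4% |

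An unstructured covariance gave 4.8% to 5.2% for both contrasts in all of these complete-data scenarios.

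**Carry-forward alone.** If an assumed 10, 30 or 50% of patients have values carried forward, unrelated to their creatinine, the change test under compound symmetry runs at 5.2, 5.9 or 6.7%. The level test stays at 4.9% to 5.0%.

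**Closer to the planned analysis.** Full REML with Kenward-Roger degrees of freedom, three sites of assumed near-equal size as a fixed effect, and 8 of 88 patients dropping out at random (88 enrolled, 80 needed; 10,000 trials per cell, SE about 0.2 point):

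| Assumed true covariance | Compound symmetry fitted, change / level | Unstructured fitted, change / level |
|---|---|---|
| Compound symmetry | 4.9 / 5.3% | 5.1 / 5.2% |
| Fade 0.895/0.865/0.815 | 9.8 / 4.8% | 4.9 / 4.7% |
| AR(1) | 13.1 / 5.4% | 4.7 / 5.5% |
| SD rising 50% | 9.2 / 10.1% | 5.2 / 5.0% |
| SD 1/1.3/1.3/1 | 1.4 / 2.3% | 5.1 / 5.2% |

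All unstructured fits converged, but they were started at the true covariance.

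**The case against.** The strongest reply is that no error has been shown. A pre-specified compound-symmetry model is a legitimate choice, and it matches the two-component model used for the sample size. The pilot data may have supported it; they are not reproduced in the protocol, and reporting only two components does not prove that other structures were never compared. Robust standard errors, degrees of freedom and convergence rules are commonly left to a SAP. The largest figures concern the change, while sections 5.1.1, 6.1 and 6.2.2 lean towards the 72-hour level, for which fading correlation does no harm.

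Much of this stands. The sizes are conditional on assumed covariances, and the missing technical detail would not be a finding by itself. But the protocol does not leave the structure open: it fixes it, so a later SAP must either follow it or contradict it. The level test is not safe either, since changing spread alone moves it between 2.4% and 10.0% in the scenarios above.

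Some limits remain. Carry-forward, a departure that the protocol itself builds in, has little effect. The creatinine entry threshold in section 3.2 truncates baseline values and may be another departure; it was not examined. Non-normal data, informative drop-out and the heterogeneous Toeplitz fallback were not tried.

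**Conclusion.** The concern holds as an unguarded risk. The protocol fixes a covariance structure for the primary test that its own figures presuppose and cannot check. If the structure is wrong, the nominal 5% test can be too liberal or too conservative, and the document does not show which, so no direction is claimed. A mild departure is enough to matter for the change: lag correlations running only from 0.885 to 0.845 raise its type I error to 7.4%. All sizes rest on the assumed covariances, on reading 0.19 and 1.3 as random-intercept components, and on normal data without informative drop-out. The change should be made, with medium confidence in its practical importance.

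**What to change.** In section 6.2.2, replace the covariance sentence with:

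> An unstructured covariance matrix will be used, with Kenward-Roger degrees of freedom. If the model does not converge, heterogeneous Toeplitz and then compound symmetry with a robust (sandwich) standard error will be used, in that order.

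If the details are kept for a SAP, it is enough to name the unstructured matrix here. Use the same wording in section 6.2.3 for consistency only; the protocol gives no lactate variance, so no size is claimed there. The last fallback, simulated with an uncorrected sandwich standard error on 86 degrees of freedom, gave 5.1% to 5.5%.

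**Cost.** Visits and sample size do not change. There are 10 covariance parameters instead of 2, and the degrees of freedom for the change fall from 258 to 86 (from 243 to about 82 with 8 of 88 dropping out).
- If compound symmetry is true, the interval is 0.8% wider for the change and 0.2% wider for the level. Power for a change of 0.51 at 44 per arm is 97.0% instead of 97.2%.
- If correlation fades, the interval for the change is wider because it is honest: by 21% at 0.895/0.865/0.815 and 33% under AR(1). Power is then 89% and 83%, not the 97% that a compound-symmetry calculation implies.
- If the spread peaks mid-course, the interval is narrower: by 12% to 19% for the change and 9% to 14% for the level.

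The change should be made before unblinding.
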